## **Exercises intervention program**

Exercise intervention is implemented in the gym room at the Community Health Service Center. The room was equipped with multiple devices for both aerobic and resistance training, which allowed a maximum of six participants to perform exercise at the same time. Room temperature is between 18-22 °C, controlled

by air conditioning. The training program is designed to take place three times a week for a total of eight weeks. Exercise intervention is scheduled for approximately 70 minutes per session (30 minutes of aerobic and 30 minutes of resistance, no break between two types, 5-min of preparation and 5-min relaxation stretching movements before and after each intervention), performed between 8:00 to 11:00 or between 14:00 to 16:30, Monday through Saturday. Exercise sessions starts at least 30 minutes after meals.

The target heart rate during aerobic exercise is set as resting heart rate (HR) + 40%-70% of heart rate reserve (HRR). Participants' HRR was calculated based on their resting HR and maximum heart rate ( $HR_{max}=208-0.7\times age$ ) as  $HR_{max} - HR$ . Heart rate monitors (OH1, Polar Oy, Oulu, Finland) are used during all exercise sessions to track exercise intensity and ensure that it remained within the specified range. Aerobic exercise is performed on bicycle ergometers (Ergoselect 100K, Ergoline GmbH, Bitz, Germany) for a continuous 30 minutes with a progressive intensity of 40%-70% HRR. Resistance level is set according to an adaptive training prior to the first intervention, pedal cadences are 50-60r/min.

Resistance exercise is conducted using a set of equipment (Nanjing Kuanyue Health Technology Co., Ltd, Nanjing, China) including chest press/ row, leg extension/ curl, abdominal/ back, biceps/ triceps, inner/ outer thigh, and push/ pull machines. Prior to conducting the 1 repetition maximum (RM) testing for the major muscles of the upper and lower limbs, all participants receive proper instructions on how to use the equipment. The Brzycki 1-RM prediction equation is used to estimate the 1RM based on the recorded resistance and repetitions. All participants performed resistance exercise with a weight of 60%-80% 1RM. Movements on each machine are repeated 10-12 times per unit for a total of 4 units, with a 30 second break between units. Resistance training involves progressive overload over an 8-week period.

In all intervention sessions, participants in AR group complete aerobic exercise before starting resistance exercise, while participants in RA group perform two types of exercise in a reversed order. Participants are instructed to maintain their usual lifestyle but refrain from engaging in other forms of regular exercise throughout the intervention period. Prior to enrollment and during the intervention period, weekly dietary guidance on diabetes management is delivered by a dietitian from the Community Health Service Center to minimize the possibility of dietary changes during the intervention.

### **Statistical analysis plan**

A sample size of 54 participants is considered adequate to achieve 95% power for detecting within-between interactions, using measures taken at pre- and post-intervention time points, based on a medium effect size ( $f = 0.25$ , G\*Power, version 3.0.10). Analyses are carried out following the intention-to-treat principle. The personnel who conduct the analyses are blinded about participants' randomization group. Data are checked for normality by using the Shapiro-Wilk test. Between group comparisons of the outcome variables are

conducted using analysis of covariance (ANCOVA), controlling for the baseline value of the variable of interest, while within-group pre-post-intervention comparisons are performed using paired samples t-tests. Between-group comparisons of non-normally distributed outcome variables are conducted using the Mann-Whitney U test, and within-group comparisons are conducted using the Wilcoxon signed-rank test. Repeated measures analysis of variance (ANOVA) is used to analyze blood glucose levels at various time points during exercise and recovery periods (90 minutes post-exercise), including the main effects of time and group, as well as interaction between time  $\times$  group. Additionally, the change rates of overnight blood glucose levels recorded by CGM on non-exercise days are analyzed for the main effect of group. Between group comparisons of baseline values are analyzed using independent samples t-tests, Mann-Whitney U test, or chi-square test. All tests are two-tailed, P values  $< 0.05$  are considered statistically significant. All analyses are performed using SPSS statistical software version 26 (IBM Corp., Armonk, NY, USA).

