## **Randomization**

Participants are randomized in a 1:1 ratio into aerobic-then-resistance exercise group (AR, n=28) and resistance-then-aerobic exercise group (RA, n=28). Randomization is stratified by age and HbA1c ( $\leq$  or  $>$ medians) with a block size of 4.

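### Does the 95% power figure, computed for a pre-post interaction, misdescribe the planned ANCOVA?

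*Combined protocol and SAP*

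**What the plan says.** The sample-size sentence in the Statistical analysis plan reads "A sample size of 54 participants is considered adequate to achieve 95% power for detecting within-between interactions". The effect size behind it is f = 0.25, labelled medium, for one measurement before and one after the programme, with G*Power given as the source. The sentence names no outcome, SD, raw difference or pre-post correlation.

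The same section compares the arms on the outcome variables by a model "conducted using analysis of covariance (ANCOVA), controlling for the baseline value of the variable of interest". For skewed outcomes, "Between-group comparisons of non-normally distributed outcome variables are conducted using the Mann-Whitney U test". A time-by-group interaction appears only in the repeated-measures ANOVA, which "is used to analyze blood glucose levels at various time points during exercise and recovery periods (90 minutes post-exercise"). On error control, "All tests are two-tailed", with 0.05 as the threshold. The Randomization section allocates 28 participants to each arm, so 56 are randomised against the 54 in the calculation.

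**The concern.** Three things look wrong together.

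- **Unstated input.** The power of a pre-post interaction test depends on the correlation between the two measurements, and the plan gives none.
- **The effect-size label.** In a plain two-group comparison, f = 0.25 is a difference of 0.5 SD. In a two-group, two-time interaction the same f is a 1.0 SD difference in change. The word medium does not show which is meant.
- **The test.** The calculation is for an interaction, while the pre-post arm comparison is an ANCOVA or a Mann-Whitney test.

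At stake is how a null result would be read. Both arms do the same exercise in a different order. Someone who took medium as 0.5 SD might treat a non-significant result as strong evidence that order does not matter, although the trial would detect a difference of that size only about half the time if the correlation is 0.5.

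**Working it through.** **Inputs from the plan.** N = 54 (56 randomised), two equal arms, two time points, f = 0.25, two-sided alpha 0.05, target power 95%.

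**Inputs assumed here.** Pre-post correlation rho = 0.5, range 0.3 to 0.7, with zero as the extreme; equal SD at both times. A 0.5 SD difference is used only for comparison. The documents give none of these.

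**1. Reproduce the plan's figure.** For the interaction, the noncentrality is lambda = f² × N × 2 / (1 − rho), with 1 and N − 2 degrees of freedom. At rho = 0.5:

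lambda = 0.0625 × 54 × 2 / 0.5 = 13.5, with 1 and 52 df, giving power 95.0%.

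N = 52 gives 94.2% and N = 53 gives 94.6%, so 54 is the smallest number that reaches 95%. Other correlations at N = 54:

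| rho | 0 | 0.3 | 0.4 | 0.5 | 0.6 | 0.7 |
|---|---|---|---|---|---|---|
| Interaction power | 72.2% | 86.2% | 90.9% | 95.0% | 98.1% | 99.7% |

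The correlation must be at least 0.50 for 54 participants, or about 0.48 for 56.

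**2. Translate f.** In a 2 × 2 layout, an interaction f of 0.25 shifts each cell by 0.25 SD up or down. The between-arm difference in change is 4 × 0.25 = 1.0 SD of a single measurement.

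**3. Power of the planned ANCOVA.** For a difference of D SD, lambda = D² × (N/4) / (1 − rho²), with 1 and N − 3 degrees of freedom. At D = 1.0, rho = 0.5 and N = 54:

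lambda = 13.5 / 0.75 = 18.0, giving power 98.6%.

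At D = 0.5, lambda = 4.5, giving 54.8%. Averaging over chance baseline imbalance lowers both by less than one point. The averaged values at N = 54 are:

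| rho | 1.0 SD | 0.5 SD |
|---|---|---|
| 0 | 94.6% | 43% |
| 0.3 | 96.2% | 46% |
| 0.5 | 98.4% | 54% |
| 0.7 | 99.9% | 71% |

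At 1.0 SD the zero-correlation figure is 95.0% without the averaging, and 95.3% (averaged) if all 56 are evaluable. Simulation with 20,000 trials agrees: 96.3%, 98.4% and 99.9% at 1.0 SD for rho of 0.3, 0.5 and 0.7.

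**4. Compare the two tests at the plan's own effect.** At 1.0 SD the ANCOVA exceeds the interaction test at each correlation examined: 96.2% against 86.2% at 0.3, 98.4% against 95.0% at 0.5, and 99.9% against 99.7% at 0.7. The ANCOVA also removes the dependence that caused the worry, since it needs no particular correlation to reach about 95%.

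**5. The Mann-Whitney route.** Simulated on normal data at N = 54 and 1.0 SD, it gives about 94% on post values. On change scores it gives 84%, 94% and 99.5% for rho of 0.3, 0.5 and 0.7. This is only illustrative, because the plan reserves the test for non-normal outcomes.

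**The case for a change.** The strongest case for a change is that this sentence is the plan's only justification of sample size and gives no power for the comparison that will be reported. Nothing tells the reader that the target is 1.0 SD, and nothing justifies so large a difference between arms that differ only in exercise order. With 54 evaluable participants the expected 95% confidence interval half-width is about 0.48 SD at a correlation of 0.5 (0.52 to 0.39 for 0.3 to 0.7). An observed difference of zero would therefore leave differences of nearly half an SD open. One paragraph would make this plain at no cost in participants.

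Much of this stands as fact: the correlation is not written down, f = 0.25 does mean 1.0 SD here, and no ANCOVA power is given. It does not amount to a fault in the design. The plan states the test family, the two time points, f and the software, which is enough to recover the calculation once the correlation is taken as 0.5. The 54% figure answers a question the plan does not pose: it needs a 0.5 SD target and a correlation that are both assumed here. The documents give no smallest important difference, so they cannot show that 1.0 SD is too large or that 0.5 SD is the right benchmark. The caution about a null result is met by reading the confidence interval when results are reported, whatever this sentence says.

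**Conclusion.** The concern does not call for a change. The sample-size figure is correct at a correlation of 0.5. Replacing the interaction by a baseline-adjusted ANCOVA loses no power for the effect the plan chose: about 98% at a correlation of 0.5 and about 95% at worst, against 95% claimed. With randomised arms, both tests address the same between-arm difference.

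What remains is a reporting gap. The assumed correlation and the 1.0 SD meaning of f could be written beside the calculation, but doing so would alter no sample size, analysis or result.

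The conclusion rests on roughly normal outcomes with equal SD at both times, and on about 54 evaluable participants. For outcomes sent to the Mann-Whitney test, power at 1.0 SD could fall below 95%, and normal-data simulation cannot settle by how much. The 54% (46% to 71%) at 0.5 SD is a fair description of what this trial can do for a smaller difference, but it is not a failure to deliver the power the plan states.

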## **Continuous glucose monitoring**

Participants undergo a 14-day continuous glucose monitoring (CGM, FreeStyle libre Pro, Abbott Diabetes Care Ltd, Witney, UK) started at two time points: one week before initializing the exercise intervention and at the 8th week of the intervention. An ambulatory glucose monitoring sensor is attached to the posterior aspect of the participants' non-dominant arm, with a guide needle implanted into the subcutaneous tissues. Sensor attachment is manipulated by a research assistant at the study site, between 8:00 to 10:30 on the same day of blood sample collection. Participants do not have access to their own CGM data during the monitoring periods. Following the monitoring period, data are exported and saved from the sensor using scanner of the CGM system by a research assistant at the study site. CGM data collected starting from 00:00 on the second day following the sensor attachment until 00:00 on the day of sensor detachment are included in the analyses.

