## **Assessments of regular glycemic outcomes and covariates**

Baseline information included age, sex, duration of T2D, and medication are obtained by the specialist physician during the recruitment procedure. Prior to the exercise intervention, participants' body mass index (BMI) and blood pressure were measured at the study site. Measurements of participants' fasting plasma glucose, fasting insulin, and hemoglobin A1c (HbA1c) are taken within the week before and after an 8-week exercise intervention. Following an overnight fasting period of  $\geq 8$  hours, 10 ml of venous blood is collected before breakfast (7:00-8:00), and tested by the Laboratory Department of the Community Health Service Center.

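### The plan claims intention-to-treat, but does not secure follow-up of participants who stop training, and its named tests use observed values only

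*Combined protocol and SAP*

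**What the plan says.** On the analysis population, the Statistical analysis plan section has one sentence: "Analyses are carried out following the intention-to-treat principle". It gives no definition of the analysis set, no rule for missing outcomes and no sensitivity analysis.

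The timing of follow-up is set in two other sections:

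- **Continuous glucose monitoring:** the two 14-day recordings start "one week before initializing the exercise intervention and at the 8th week of the intervention".
- **Assessments of regular glycemic outcomes and covariates:** fasting glucose, fasting insulin and HbA1c "are taken within the week before and after an 8-week exercise intervention".

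The Exercises intervention program section gives the schedule: "The training program is designed to take place three times a week for a total of eight weeks". No section counts an assessment date from randomisation or from the first session. None says what happens to the assessments of someone who stops attending.

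The named analyses are:

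- **Between groups:** "conducted using analysis of covariance (ANCOVA), controlling for the baseline value of the variable of interest".
- **Within groups:** "within-group pre-post-intervention comparisons are performed using paired samples t-tests".
- **Non-normal outcomes:** "Between-group comparisons of non-normally distributed outcome variables are conducted using the Mann-Whitney U test", with the Wilcoxon signed-rank test for within-group change.
- **Session glucose:** repeated measures ANOVA "is used to analyze blood glucose levels at various time points during exercise and recovery periods".

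**The concern.** Intention-to-treat keeps each participant in the assigned arm, but it cannot supply an outcome that was never collected. A participant who stops in, say, week 3 has no follow-up visit that the protocol clearly assigns to them. Site staff could reasonably not recall them, and the named tests would then leave them out without any decision being recorded.

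The planned difference between the arms is the order of two 30-minute exercise blocks done without a break. If one order is harder to tolerate, stopping could differ by arm. The participants with observed outcomes would then no longer be the randomised groups, and the comparison would tend to favour the arm that lost more of its poorly performing participants. Because the text is silent, the analysis set could also be settled after the losses are known.

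**Working it through.** **1. The plan's own sample size.** The Statistical analysis plan section gives N = 54, 95% power, f = 0.25, two time points and two-tailed α = 0.05. The pre-post correlation ρ is not given; 0.5 is assumed here. For the within-between interaction:

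λ = f² × N × m / (1 − ρ) = 0.0625 × 54 × 2 / 0.5 = 13.5, with 1 and 52 degrees of freedom.

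Power is 0.9501, so the stated 54 reproduces. It depends on ρ: the same calculation needs 106 at ρ = 0, 76 at ρ = 0.3 and 34 at ρ = 0.7.

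**2. What lost cases do to power.** The Participants and Randomization sections give 56 in total, 28 per arm. With ρ = 0.5:

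| Complete cases | Lost of 56 | Power |
|---|---|---|
| 56 | 0 | 0.957 |
| 54 | 2 (3.6%) | 0.950 |
| 52 | 4 (7.1%) | 0.942 |
| 50 | 6 (10.7%) | 0.934 |
| 44 | 12 (21.4%) | 0.900 |

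Power declines slowly, so it is not the main issue.

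**3. What each named test needs.**

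| Analysis | Data used |
|---|---|
| ANCOVA | Participants with both a baseline and a follow-up value |
| Paired t-test, Wilcoxon signed-rank | Complete pairs |
| Mann-Whitney U | Observed values |
| Repeated measures ANOVA | In the standard SPSS general linear model, only participants with every time point |

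The plan names no imputation and no likelihood-based model. The case loss follows from how these tests normally work; the plan does not state it.

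**4. Selection bias in the complete-case difference.** Let a share p of an arm stop, and let stoppers end g SD worse than completers. The mean of the whole arm is then the completers' mean minus p × g, so the completers' mean is too favourable by p × g. With the same g in both arms:

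bias = (p₁ − p₂) × g

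The stopping counts and g are assumptions, because the documents give no figures.

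- 5 of 28 against 1 of 28, g = 1 SD: (5 − 1)/28 × 1 = 0.143 SD.
- 3 of 28 against 1 of 28, g = 0.5 SD: (3 − 1)/28 × 0.5 = 0.036 SD.

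**5. Size against sampling error.** The unadjusted standard error of the difference, in SD units, is √(1/n₁ + 1/n₂).

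- 23 and 27 completers: √(1/23 + 1/27) = 0.284, so the bias is 0.143/0.284 = 0.50 standard errors.
- 25 and 27 completers: √(1/25 + 1/27) = 0.278, so the bias is 0.036/0.278 = 0.13 standard errors.

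**6. Effect on false positives.** Complete-case ANCOVA was simulated with 28 per arm, ρ = 0.5 and no true difference among all randomised participants (20,000 runs). The 5-against-1 case gave a type I error of about 9% against the nominal 5%. The 3-against-1 case stayed a little above 5%.

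**The case against.** The strongest reply is that the plan is silent rather than contradictory. The second sensor period starts in week 8, before the programme ends, so it cannot depend on completing the programme. The wording for the blood tests can be read as a fixed eight-week calendar, in which someone who stops in week 3 still has a week 8. No section limits assessment to those who finish. If everyone returns, ANCOVA on all randomised participants is intention-to-treat as claimed.

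This stands. A reader might infer that follow-up is triggered by completing the programme, that someone who stops early cannot reach either assessment, or that the plan as written is a completers' analysis. The documents support none of these. They leave follow-up after stopping unsecured, which is a weaker statement.

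Four further points also stand:

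- Both arms do the same exercises for the same time, and the documents give no evidence of different tolerance, no dropout rate and no safety-related stopping. Such stopping is a scenario only.
- Enrolling two more than the calculated 54 is not a limit on tolerable loss, since power falls gradually.
- The assumed biases are half a standard error or less.
- Session glucose exists only where a session took place. A mixed model helps with an isolated missing reading, but not with sessions missed after stopping.

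None of this closes the gap. A calendar reading is possible but not stated, and even under it the plan does not say what is done when a participant fails to return.

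**Conclusion.** The point holds as a missing specification. The plan claims intention-to-treat, words its follow-up times relative to the intervention, does not say that participants who stop are still assessed, and names only tests that use observed values. Participants who stop can therefore drop out of the analysis; whether they would depends on site practice that the documents do not describe.

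The illustrated bias runs from 0.04 SD, which is minor, to 0.14 SD, which nearly doubles the false-positive rate. Both rest on assumed stopping counts and assumed poorer outcomes in stoppers. If stopping is balanced between arms and stoppers fall equally far behind in each, the formula gives no bias. The change is worth making because it is cheap and removes a choice that could otherwise be made after the losses are known.

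**What to change.** 1. **Timing.** Date the follow-up blood tests and the second sensor period by calendar week from each participant's first scheduled session.
2. **Collection.** State that both are collected from every randomised participant regardless of attendance, and that reasons for stopping are recorded and reported by arm.
3. **Pre-post outcomes.** Define the analysis set as all randomised participants in their assigned arm. For those who do not return, name a likelihood-based mixed model or multiple imputation. Add a sensitivity analysis, for example one in which missing outcomes are worse than predicted.
4. **Session glucose.** Replace repeated measures ANOVA with a linear mixed model, so that one missing reading does not remove the participant. This does not recover data from sessions that never took place.
5. **Otherwise.** If follow-up after stopping will not be collected, describe the analysis as complete-case.

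The cost is some added wording in the protocol and SAP, slightly more analysis, and the effort of recalling the few who stop. No new type of measurement is needed, and the exercise programme is unchanged.

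### Pre-post outcomes judged non-normal lose baseline adjustment in the between-group test; one prespecified baseline-adjusted test per outcome would be more efficient at little cost

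*Combined protocol and SAP*

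**What the plan says.** The Statistical analysis plan section makes ANCOVA the between-group analysis, "controlling for the baseline value of the variable of interest". It also states that "Data are checked for normality by using the Shapiro-Wilk test", and then: "Between-group comparisons of non-normally distributed outcome variables are conducted using the Mann-Whitney U test". No covariate, transformation, change score or rank-based ANCOVA is named for that second branch. The section does not say whether normality is judged on raw values, change scores or residuals, or whether Mann-Whitney is applied to post values or to change.

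Baselines exist for the pre-post outcomes. In the section on regular glycemic outcomes, "fasting plasma glucose, fasting insulin, and hemoglobin A1c (HbA1c) are taken within the week before and after an 8-week exercise intervention". In the Continuous glucose monitoring section, monitoring is "started at two time points: one week before initializing the exercise intervention and at the 8th week of the intervention".

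The sample size is set for "95% power for detecting within-between interactions, using measures taken at pre- and post-intervention time points, based on a medium effect size". On blinding: "The personnel who conduct the analyses are blinded about" the allocation.

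**The concern.** Whether an outcome is adjusted for its baseline depends on a normality p-value. An outcome that fails the check gets no baseline-adjusted estimate, so outcomes in the same report may be compared on different footings.

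The trial was sized for a group-by-time interaction, which with two time points is a comparison of change. Mann-Whitney on change scores still uses the baseline. Mann-Whitney on post values ignores it. The plan leaves this open, and the answer decides whether the loss is small or large. At stake is power for effects smaller than the one planned for. Both arms do the same exercise and differ only in its order, so a smaller effect is a reasonable possibility to plan for, though the documents give no figure for one.

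**Working it through.** **1. The plan's own figure.** Inputs from the Statistical analysis plan section: f = 0.25, N = 54, two measurements (m = 2), 95% power, two-sided 0.05 ("All tests are two-tailed"). The pre-post correlation ρ is not given; 0.5 is assumed.

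- λ = f²·N·m/(1−ρ) = 0.0625 × 54 × 2/0.5 = 13.5. The noncentral F with 1 and 52 df gives power 0.950, so N = 54 reproduces.
- It depends on ρ: the same power needs N = 76 at ρ = 0.3 and N = 34 at ρ = 0.7.
- In a 2×2 design a between-arm difference in change of δ gives f = δ/(4·SD). So f = 0.25 means δ = 1.0 SD.

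**2. Simulation of the switching rule.** 28 per arm (Randomization section), 5,000 trials per setting, Monte Carlo SE at most √(0.25/5000) = 0.7 points. Rule: Shapiro-Wilk p < 0.05 in either arm leads to Mann-Whitney, otherwise raw-scale ANCOVA. Both tests use change scores in one reading and post values in the other. Skew and correlation are assumptions.

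Power (%), lognormal with log-SD 0.6, effect on the log scale, at ρ = 0.5/0.7/0.8:

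| Effect | Rule, change scores | Rule, post values | Rank ANCOVA | Log ANCOVA |
|---|---|---|---|---|
| 1.0 SD | 97/100/100 | 94/94/95 | 98/100/100 | 98/100/100 |
| 0.7 SD | 75/91/97 | 71/71/72 | 82/92/98 | 85/95/99 |
| 0.5 SD | 45/64/80 | 42/43/44 | 52/67/82 | 56/72/87 |

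Loss against rank ANCOVA, by subtraction from the rounded table:

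- Change scores: 7/1/1 points at 0.7 SD and 7/3/2 at 0.5 SD.
- Post values: 11/21/26 points at 0.7 SD and 10/24/38 at 0.5 SD.

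A separate run of 1,000 trials per setting at 0.5 SD gave 45/63/80 (change) and 44/42/43 (post) against 54/67/80, that is, losses of 9/4/0 and 10/25/37. At 1.0 SD the rule kept 93% or more. Together the runs give about 0-9 points on change scores and 10-38 on post values.

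**3. Other shapes, 0.7 SD, same order of ρ.**

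| Shape | Rule, change scores | Rule, post values | Rank ANCOVA |
|---|---|---|---|
| Normal | 82/94/99 | 82/92/96 | 80/92/98 |
| Lognormal, log-SD 0.3 | 80/93/98 | 76/81/82 | 80/92/98 |
| Lognormal, log-SD 0.8 | 74/89/97 | 71/69/70 | 82/92/98 |
| Gamma, shape 2 | 81/95/99 | 85/85/84 | 91/98/99 |
| t, 3 df | 93/99/100 | 93/94/95 | 96/99/100 |

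On change scores nothing is lost under normal or mildly skewed data. The largest loss on that reading is 91 − 81 = 10 points (gamma, ρ = 0.5).

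Raw-scale ANCOVA is not a safe universal replacement: at log-SD 0.8 it has 70/82/91%, below the change-score rule's 74/89/97%.

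**4. How often the fallback applies** (change scores; post values): normal 9-10% for both; log-SD 0.3, 24-34% and 56-58%; log-SD 0.6, 66-86% and 96-97%.

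**5. Type I error.** Overall, the rule rejects a true null in 4.1-5.8% of trials in every setting. Given a chance baseline difference of 2 SE (SE = √(2/28) = 0.267 SD; no effect, log-SD 0.6), the rates are 12-23% on post values, 7-10% on change scores and 4-6% for rank ANCOVA. Lower rates when the arms are balanced offset these.

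**6. Stratification.** The Randomization section stratifies HbA1c at its median. For a normal baseline split at the median, the within-half SD is √(1 − 2/π) = 0.603, so the SE of the HbA1c difference falls to about 0.603 × 0.267 = 0.16 SD. An imbalance of 2 × 0.267 = 0.53 SD is then about 3.3 SE and occurs in about 0.1% of trials, against about 4.6% without stratification.

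**The case against.** The other side has a strong case, and much of it stands.

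- **The fallback is prespecified, analysts are blinded and Type I error is held.** This stands. A reader might infer that the switch invalidates the test or inflates false positives. The plan and the simulations do not support that.
- **Little is lost at the design effect.** This stands for correlations of 0.5-0.8. A reader might infer that the trial is underpowered because of the switch; at 1.0 SD it is not. The case for change rests on smaller effects, which the plan did not target.
- **The large losses need several assumptions at once:** post values, marked skew, correlation of 0.7-0.8 and an effect below 1.0 SD. The documents state none of these. But the plan does not rule out post values either, and that is the open detail.
- **The comparator is favoured.** Ranks are unchanged by a log transformation, so the lognormal model helps rank ANCOVA against raw change scores. This stands; the change-score losses should be read with it in mind.
- **The form of the normality check matters.** Testing ANCOVA residuals instead (post values, ρ = 0.7, 0.7 SD) raises the rule from 80% to 85% against 91% for rank ANCOVA at log-SD 0.3. At log-SD 0.6 the gap remains (75% against 93%).
- **Imbalance.** A reader might apply the 12-23% false-positive rates to HbA1c. Stratification makes such an imbalance very rare there. The rates matter only for outcomes weakly related to HbA1c.
- **Scope.** A reader might infer that every between-group comparison should be baseline-adjusted. Baseline tests cannot be, and no pre-intervention value is documented as a covariate for the in-exercise glucose series or the overnight rates of change.

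**Conclusion.** The point holds as one of efficiency and of a missing baseline-adjusted estimate, confined to pre-post outcomes with a measured baseline. It is worth changing because the baselines are already collected and the remedy is wording, but it does not threaten validity.

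Under assumed lognormal data (log-SD 0.6, ρ 0.5-0.8) and effects of 0.5-0.7 SD, the loss against rank ANCOVA is about 0-9 points if Mann-Whitney uses change scores and about 10-38 if it uses post values. At 1.0 SD, power is about 93% or more on either reading in that range.

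These sizes rest on skew, correlation and smaller effects that the documents do not give. Below ρ = 0.5, change scores do worse: with Mann-Whitney applied directly to lognormal data (ρ = 0.3, 0.5 SD, 27 per arm), power was 32% on change scores against 45% for rank ANCOVA. At 1.0 SD with 28 per arm it was 88.5% against 95.8%. Confidence in the size is medium.

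**What to change.** Replace the unadjusted Mann-Whitney fallback with one baseline-adjusted between-group test per pre-post outcome, named before unblinding. Suggested text:

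> Each pre-post outcome with a measured baseline is compared between groups by ANCOVA adjusting for that baseline, on a scale listed for the outcome before unblinding. The scale is raw or, for outcomes expected to be right-skewed such as fasting insulin, logarithmic for both outcome and baseline, reported as a ratio of geometric means. Where no scale can be justified, rank ANCOVA (ranked outcome on ranked baseline) is the named test. Normality is assessed on residuals and reported; it does not change the method. Any other between-group test is supplementary. If Mann-Whitney is reported, it is stated whether it uses post values or change scores.

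Naming a single test per outcome avoids two results with no rule for disagreement. The text should not extend to baseline tests, nor to the in-exercise glucose series or overnight rates of change unless a pre-intervention value exists.

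Cost: SAP wording only; log-scale and rank ANCOVA both run in SPSS 26. Downsides: log-scale results are ratios, and rank ANCOVA gives no effect in clinical units. Rank ANCOVA can also lose power to the planned rule: 85.7 − 80.4 = about 5 points with normal data, and 83.2 − 80.3 = about 3 points at log-SD 0.3 (both at 0.5 SD, ρ = 0.8).
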